6.5.4. Physical examination

A complete physical examination will be performed at screening and follow-up visits and will include an assessment of the following: general appearance, respiratory, CV, abdomen, skin (for signs of injection site reactions due to MEDI0457 or EP), lymph nodes, abdomen, pelvis, musculo-skeletal, and neurological systems. A targeted physical examination to document changes in any medical condition since the last visit will be performed at all other visits.

6.5.5. WHO/ECOG performance status

A WHO/ECOG performance status will be conducted at screening and at follow-up. A WHO/ECOG performance status will be performed at other visits as determined by investigator or directed per patient complaints.

WHO/ECOG performance status (Oken et al 1982) will be assessed based on the following:

- 0=Fully active; able to carry out all pre-disease performance without restrictions.
- 1=Restricted in physically strenuous activity but ambulatory and able to carry out light work or work of a sedentary nature, e.g., light housework, office work.
- 2=Ambulatory and capable of self-care but unable to carry out any work activities. Up and about more than 50% of waking hours.
- 3=Capable of only limited self-care, confined to bed or chair more than 50% of waking hours.
- 4=Completely disabled. Unable to carry out any self-care and totally confined to bed or chair.
- 5=Dead

Any significant changes from baseline or screening must be reported as an AE.

6.5.6. Post-treatment reaction assessment

The investigator will assess local and systemic reactions post-treatment (within 30-60 minutes after study treatment). Any reported MEDI0457 local post-treatment reactions and systemic post-treatment reactions will be graded per NCI CTCAE version 4.03 and all must be recorded in the database. See **Appendix E** for more information.

6.5.7. Vital signs

Vital signs including temperature, respiration rate, pulse oximetry, blood pressure, HR and weight will be measured at all the study visits.

Version Number: 1.8

Proprietary of MD Anderson Cancer Center Date: July 26, 2019

On infusion days, patients receiving durvalumab treatment will be monitored during and after infusion of IP as present in the bulleted list below.

Supine blood pressure will be measured using a semi-automatic blood pressure recording device with an appropriate cuff size, after the patient has rested for at least 5 minutes. Blood pressure and pulse will be collected from patients receiving durvalumab before, during and after each infusion at the following times (based on a 60-minute infusion):

- Prior to the beginning of the infusion (measured once from approximately 30 minutes before up to 0 minutes [i.e., the start of the infusion]).
- Approximately 30 minutes (\pm 5 minutes) after start of the infusion (half way through the infusion).
- At the end of the infusion (approximately 60 minutes \pm 5 minutes).
- A 1 hour (± 15 minutes) observation period is required after the first infusion of durvalumab is administered.

If no clinically significant infusion reactions are observed during or after the first dose, the length of subsequent infusion observation periods can occur at the investigator's discretion (suggested 30 minutes after each durvalumab infusion). If the infusion duration exceeds 60 minutes, then blood pressure and pulse measurements should follow the principles as described above or be obtained more frequently if clinically indicated. The date and time of collection and measurement will be recorded in the database. Additional monitoring with assessment of vital signs is at the discretion of the investigator per standard clinical practice or as clinically indicated.

6.5.8. Electrocardiogram

An ECG will be performed at screening within 28 days prior to Cycle 1 Day 1 for all patients to determine patient eligibility and as clinically indicated throughout the study. One 12-lead ECG recordings is required at the screening visit.

The following parameters will be recorded for each ECG: date and time of ECG, HR (beats/min), PR interval (ms), RR interval (ms), QRS interval (ms), QT interval (ms), QTcF interval (for Fridericia's) (ms), sinus rhythm (yes/no), and overall evaluation (normal/abnormal).

Abnormal ECGs should be interpreted as clinically significant or not clinically significant.

In case of clinically significant ECG abnormalities, including a QTcF value > 470 ms, two additional 12-lead ECGs should be obtained over a brief period (e.g., 30 minutes) to confirm the finding.

6.6. Biological Sampling Procedures

A summary of the samples collected and planned analyses for the study is presented in **Table 4**. The approaches to perform these research assays are rapidly evolving in the laboratories at the MD Anderson Cancer Center and across the world. Thus, we will perform these analyses with the current state-of-the-art assays available at the time of analysis.

Version Number: 1.8 Date: July 26, 2019

Proprietary of MD Anderson Cancer Center

Table 4. Summary of Samples, Target, and Assays

Sample	Target	Assay
Tumor (Archival/Biopsy)	HPV-16/HPV-18 genotyping	HPV16/18 assay
Tumor (Biopsy)	HPV-16/HPV-18 DNA sequence	DNA sequencing
Tumor (Biopsy)	PD-L1, p16 expression and exploratory biomarkers	IHC, Nanostring, RNAseq, or Affymetrix expression analysis
Serum	HPV-16/HPV-18 E6/E7 antibodies, PK, ADA	Serology assays
PBMCs	HPV-16/HPV-18 E6/E7 T-cells	IFN-γ ELISPOT and FACS
Plasma	HLA type, Tumor cell DNA and HPV-16/HPV-18 DNA	High resolution class I HLA, PCR and DNA sequencing

6.6.1. Tumor biopsies

Patients will have a pre-treatment tumor biopsy if it can be done safely (as judged by the investigator) during screening. Week 10 Day 1 (\pm 3 days) tumor biopsies will be required until 10 subjects who completed a pre-treatment biopsy have successfully been biopsied again, and then the Week 10 biopsy will be made optional. Optional biopsies upon confirmed PD will be collected if clinically feasible (i.e., repeat biopsy does not pose unacceptable medical risk to a subject as determined by the investigator). If additional clinically indicated biopsies will be performed (e.g., for mixed responses), additional tissue will be collected for research purposes (optional). All optional biopsies will be discussed with the subject at the time of initial consent.

To confirm eligibility, tumor tissue from the subject must be confirmed positive for HPV-16 or HPV-18 according to the institutionally approved HPV 16/18 assay. Archival tissue, if available, may be used for this assay, else tissue from the screening tumor biopsy will be used.

Fresh tumor biopsies should be preferentially obtained from tumor tissues that are safely accessible as determined by the investigator and are not obtained from sites that require significant risk procedures, which include, but are not limited to, biopsies of the brain, lung, mediastinum, pancreas, or endoscopic procedures extending beyond the esophagus, stomach, or bowel wall.

The biopsied tumor lesion should not be used as a RECIST target lesion. When feasible and depending on the tumor volume, up to 5 cores (18 GA or larger) will be obtained and processed in the following preferential order: 1) FFPE, 2) fresh frozen, 3) FFPE, 4) fresh frozen, and 5) fresh frozen.

6.6.2. Research Blood

Research blood sample will be collected at the time points listed in the Schedule of Procedures (**Table 3**). These samples will be used for pharmacokinetics, pharmacogenetics, ADA, biomarker, and other analyses as described in **Section 6.6**.

Version Number: 1.8 Date: Inly 26, 2019 Proprietary of MD Anderson Cancer Center

6.6.2.1. **Immune Profiling and HPV serology**

At the time points listed in **Table 3**, up to 70 mL of blood will be collected in vacutainer tubes (containing heparin and/or serum separating agent) for the isolation of PBMCs, plasma, and serum.

6.6.2.2. PK and ADA

At the time points listed in **Table 3**, up 10 mL of blood will be collected in vacutainer tubes (containing serum separating agent) for the isolation of serum for PK and ADA analyses.

6.6.3. Withdrawal of informed consent for donated biological samples

If a patient withdraws consent to the use of donated biological samples, the samples will be disposed of/destroyed, and the action documented. If samples are already analyzed, the researchers are not obliged to destroy the results of this research.

6.7. Management of IP-related Toxicities

6.7.1. **Dose Management**

Either treatment may be stopped by the investigator while the other treatment continues. MEDI0457 doses should not be modified.

For AEs that are considered at least partly due to administration of durvalumab the following dose adjustment guidance may be applied:

- Treat each of the toxicities with maximum supportive care (including holding durvalumab).
- If the symptoms promptly resolve with supportive care, consideration should be given to continuing the same dose of durvalumab along with appropriate continuing supportive care. If medically appropriate, dose modifications are permitted for durvalumab.
- All dose modifications should be documented with clear medical reasoning and documentation of the approach taken.

In addition, there are certain circumstances in which durvalumab should be permanently discontinued (Appendix D, Postow 2015).

Following the first dose of durvalumab, subsequent administration of durvalumab can be modified based on toxicities observed (Appendix D, Postow 2015). All toxicities will be graded according to NCI CTCAE version 4.03.

Based on the mechanism of action of durvalumab leading to T-cell activation and proliferation, there is the possibility of observing irAEs during the conduct of this study. Potential irAEs include immune-mediated dermatitis, hepatitis/hepatotoxicity, endocrinopathy (hypothyroidism, hyperthyroidism, hypophysitis, and adrenal insufficiency), neuropathy/neuromuscular toxicity, nephritis, pancreatitis (elevated lipase/amylase), pneumonitis, and colitis. Patients should be monitored for signs and symptoms of irAEs. In the absence of an alternate etiology (e.g., infection or PD) signs or symptoms of dermatitis, hepatitis/hepatotoxicity, endocrinopathy

Version Number: 1.8

Proprietary of MD Anderson Cancer Center Date: July 26, 2019

(hypothyroidism, hyperthyroidism, hypophysitis, and adrenal insufficiency), neuropathy/neuromuscular toxicity, nephritis, pancreatitis (elevated lipase/amylase), pneumonitis, and colitis should be considered to be immune-related.

Dose modifications will not be required for AEs that are clearly not attributable to durvalumab (such as an accident) or for laboratory abnormalities that are not deemed to be clinically significant. Administration may continue despite concurrent vitiligo of any AE grade.

Acetaminophen and/or an antihistamine (e.g., diphenhydramine) or equivalent medications per institutional standard may be administered prior to infusion at the discretion of the investigator for primary prophylaxis against infusion-related reactions. In the event of Grade ≤ 2 infusion-related reaction, the infusion rate of durvalumab may be decreased by 50% or interrupted until resolution of the event (up to 4 hours) and re-initiated at 50% of the initial rate until completion of the infusion. In patients experiencing Grade ≤ 2 infusion-related reaction, subsequent infusions may be administered at 50% of the initial rate. If a patient experiences an infusion-related reaction, acetaminophen and/or an antihistamine (e.g., diphenhydramine) and/or corticosteroid or equivalent medications per institutional standard may be administered prior to subsequent infusions at the discretion of the investigator for secondary prophylaxis of infusionrelated reactions. If the infusion-related reaction is Grade 3 or higher in severity, treatment with durvalumab will be discontinued.

As with any antibody, allergic reactions to dose administration are possible. Appropriate drugs and medical equipment to treat acute anaphylactic reactions must be immediately available, and study personnel must be trained to recognize and treat anaphylaxis. The study site must have immediate access to emergency resuscitation teams and equipment in addition to the ability to admit patients to an intensive care unit if necessary.

6.7.2. **Dose-limiting Toxicities**

Grading of DLTs will be according to the NCI CTCAE version 4.03.

A DLT will be defined as any Grade 3 or higher treatment-related toxicity that occurs during the DLT evaluation period (i.e., 4 weeks after the first dose of durvalumab is administered for the initial six patients), including the following treatment-related toxicities:

- a. Any Grade 4 irAE is a DLT.
- b. Any \geq Grade 3 colitis is a DLT.
- c. Any \geq Grade 3 non-infectious pneumonitis irrespective of duration is a DLT.
- d. Any Grade 2 pneumonitis that does not resolve to \leq Grade 1 within 3 days of the initiation of maximal supportive care is a DLT.
- e. Any \geq Grade 3 neurotoxicity (to include but not limited to limbic encephalitis, autonomic neuropathy, including peripheral neuromotor syndromes such as myasthenia gravis and Guillain-Barré) irrespective of duration is a DLT.
- f. Any \geq Grade 3 cardiotoxicity (to include but not limited to arrhythmias, myocarditis with cardiomyopathy, ventricular dysfunction) irrespective of duration is a DLT.
- g. Any \geq Grade 3 ocular toxicity (including but not limited to iritis, uveitis, significant vision changes) irrespective of duration is a DLT.

Version Number: 1.8 Date: July 26, 2019

Proprietary of MD Anderson Cancer Center

- h. Any ≥ Grade 3 irAE, excluding colitis or pneumonitis or neurotoxicity or cardiotoxicity and ocular toxicity as mentioned above, that does not downgrade to Grade 2 within 3 days after onset of the event despite optimal medical management including systemic corticosteroids or does not downgrade to ≤ Grade 1 or baseline within 14 days.
- i. AST or ALT elevation $> 8 \times ULN$ or TBL $> 5 \times ULN$.
- j. Any \geq Grade 3 non-irAE, except for the exclusions listed below.
- k. Grade 3 or greater injection site reaction that is persistent beyond 5 days or does not downgrade to ≤ Grade 1 in 14 days.
- 1. Grade 3 or greater fever, not associated with above listed events (a to f), assessed by Principal Investigator as related to study treatment.
- m. Grade 3 or greater systemic symptoms, not associated with above listed events (a to e), assessed by Principal Investigator as related to study treatment.
- n. Any Grade 3 or greater anaphylaxis related to study treatment.
- o. Death that is at least possibly related to the study treatment.

The DLT definition excludes the following conditions:

- a. Grade 3 fatigue lasting ≤ 7 days.
- b. Grade 3 endocrine disorder (thyroid, pituitary, and/or adrenal insufficiency) that is managed with or without systemic corticosteroid therapy and/or hormone replacement therapy and the patient is asymptomatic.
- c. Grade 3 inflammatory reaction attributed to a local anti-tumor response (e.g., inflammatory reaction at sites of metastatic disease, lymph nodes, etc.).
- d. Concurrent vitiligo or alopecia of any AE grade.
- e. Grade 3 infusion-related reaction (first occurrence and in the absence of steroid prophylaxis) that resolves within 6 hours with appropriate clinical management.
- f. Grade 3 or 4 neutropenia that is not associated with fever or systemic infection that improves by at least one grade within 3 days. Grade 3 or Grade 4 febrile neutropenia will be a DLT regardless of duration or reversibility.
- g. Grade 3 or 4 lymphopenia.
- h. Grade 3 thrombocytopenia that is not associated with clinically significant bleeding that requires medical intervention, and improves by at least one grade within 3 days.
- i. Isolated Grade 3 electrolyte abnormalities that are not associated with clinical signs or symptoms and are reversed with appropriate maximal medical intervention within 3 days.

Immune-related AEs are defined as AEs of immune nature (i.e., inflammatory) in the absence of a clear alternative etiology. In the absence of clinical abnormality, repeat laboratory testing will be conducted to confirm significant laboratory findings prior to designation as a DLT.

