1.6. Study Design

This study will be an open label, multi-cohort, phase II trial for the combination therapy of MEDI0457 (INO-3112) and Durvalumab (MEDI4736) in patients with HPV-16 and/or -18 related malignancies. This study will enroll 3 cohorts of patients with HPV-16/18 (+) tumors. The three cohorts are:

- 1. HPV-16/18 cervical cancer,
- 2. HPV-16/18 rare tumors (anal, penile, vulvar, vaginal), and
- 3. HIV (+) HPV-16/18 malignancies (any site).

Each cohort will have a two-stage design with predetermined stopping rules based on ORR after stage I and each cohort will function independently clinically. After each cohort completes accrual to stage I, only the two cohorts with the most responses will move on to stage 2.

Therefore, accrual to stage 2 will not start till all three cohorts have completed stage I. However, if a single cohort has a high response rate (≥4 responses out of 9 patients), the second stage of accrual may proceed prior to other cohorts completing stage I.

At the onset of the study, only patients with cervical, vulvar, or vaginal cancers will be enrolled for the first 3 slots. Once all 3 of these patients have completed the first 6 weeks of treatment, enrollment will be opened to all included cancer histotypes.

Both MEDI0457 and durvalumab treatment will continue until confirmed disease progression or unacceptable toxicity. Either treatment may be stopped by the investigator if a SAE is deemed to be related to that treatment while the other treatment continues.

The target population consists of male or female patients 18 years of age or older with recurrent or metastatic HPV 16- or 18-associated cancers with persistent or progressive disease (PD) after initial standard-of-care treatment and lacking a curative treatment option.

Eligible patients must have at least one "measurable target lesion"—according to RECIST version 1.1—that has not been previously irradiated. In addition, if the primary lesion is not large enough for a biopsy without changing radiologic findings for following response, one additional lesion

Version Number: 1.8 Date: July 26, 2019

Proprietary of MD Anderson Cancer Center

that can be safely biopsied at screening and prior to the first dose of MEDI0457 at Week 1 will be required.

All patients will receive combination treatment with MEDI0457 and durvalumab as per the **Planned Dosing Schedule (Section 4.4.1, Figure 1**, and **Table 3**).

[figure not shown]

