Figure 1. Overall Study Design Study Flow Chart

In the case that the first stopping boundary is crossed (Section 8.1.3), a Revised Dosing Schedule will be decided by the Principal Investigators, collaborators, supporters, and IND Office Medical Monitor and will be used for the remaining patients. Two options are to decrease the number of doses of vaccine given from a total of 3 to either 1 or 2 during the first 7 weeks and/or decrease dose of durvalumab to 750 mg Q4W. Other options may also be considered based on toxicity profile.

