4.4. Doses and Treatments

4.4.1. Planned Dosing Schedule

All patients will receive combination treatment with MEDI0457 and durvalumab as per the following **Planned Dosing Schedule** (treatment should be given at the beginning of the week, unless otherwise specified) as detailed in **Figure 1** and **Table 3**.

Durvalumab will be administered at a fixed dose of 1500 mg q4wk for patients that are \ge 30 kg. For patients who weigh <30 kg, weight-based dosing will be used at a dose of 20 mg/kg q 4 weeks, and if their weight increases to \ge 30 kg they can be switched to durvalumab at 1500 mg every 4 weeks.

Patients will receive 7 mg MEDI0457 delivered by IM followed by EP on Day 1 (Week 1), Week 3, Week 7, Week 12 and then every 8 weeks until disease progression or unacceptable toxicity. Durvalumab will be administered on Week 4, Week 8, Week 12 and then every 4 weeks until disease progression or unacceptable toxicity. On days when both MEDI0457 and durvalumab administrations will occur on the same day (Week 12 then every 8 weeks), MEDI0457 will be administered first, and durvalumab IV infusion will start approximately 1 hour after MEDI0457 is delivered intramuscularly followed by EP.

Minimum time between Week 3 MEDI0457 dose and the Week 4 first durvalumab dose, and the Week 7 MEDI0457 dose and the Week 8 durvalumab dose is 7 days.

Version Number: 1.8 Proprietary of MD Anderson Cancer Center Page 1019 26 2019

4.4.2. **Durvalumab**

Durvalumab will be administered at a fixed dose of 1500 mg q4w in the combination and monotherapy arms for patients weighing \geq 30 kg. For patients weighing \leq 30 kg, the dose will be 20 mg/kg. The maximum number of doses of checkpoint inhibitor therapy will equal 13.

The duration will be approximately 1 hour (± 5 minutes) for each durvalumab infusion. A 1- hour observation period is required after the first infusion of durvalumab is administered. If no clinically significant infusion reactions are observed during or after the first dose, subsequent infusion observation periods can be at the investigator's discretion (suggested 30 minutes after each durvalumab infusion).

Patients will be monitored during and after the infusion with assessment of vital signs at the times specified in the study protocol.

See Section 6.7.1 dose administration changes in the event of Grade 1 or 2 infusion-related reactions.

4.4.3. **MEDI0457**

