8.1.1. Sample size estimate

Up to 77 evaluable patients will be enrolled in this study.

The design requires a maximum of 34 evaluable subjects per cohort. Nine subjects will be treated in the first stage. If 1 or fewer responses are seen, enrollment into that cohort will be stopped for futility. If there are 2 or more responses, an additional 25 subjects will be enrolled into the second stage. If there are 9 or more responses out of 34, the combination will be deemed worthy of further study. The two cohorts with the best response rates after completion of accrual into stage 1 for all 3 cohorts will move on to stage 2. The maximum total sample size is 77 (9 x 1 cohorts + 34 x 2 cohorts) evaluable subjects.

After each cohort completes accrual to stage I, only the two cohorts with the most responses will move on to stage 2. Therefore, accrual to stage 2 will not start till all three cohorts have completed stage I. However, if a single cohort has a high response rate (≥4 responses out of 9 patients), the second stage of accrual may proceed prior to other cohorts completing stage I.

Version Number: 1.8 Date: July 26, 2019 Proprietary of MD Anderson Cancer Center

8.1.2. **Efficacy futility assessments**

We will use a Simon's two-stage optimal design targeting an alternative hypothesis ORR of 0.35 versus a null hypothesis ORR of 0.15 with 80% power and a one-sided 0.05 significance level. This will be conducted independently in each of the three cohorts. ORR will be assessed every 8 weeks and will be defined using RECIST 1.1 criteria. During the interim, the accrual will be halted until the go/no-go decision can be made.

8.1.3. **Toxicity monitoring**

DLT will be monitored continuously in cohorts of 6 subjects for all 34 subjects to ensure safety using the methods by Thall et al. Cohorts will be monitored independently. The trial will be stopped early for toxicity if the $Pr(DLT > 30\% \mid data) > 0.90$ using a prior of beta (0.6, 1.4) for toxicity. Stopping boundaries corresponding to this probability criterion are to halt the trial if (# of patients with DLT) / (# patients evaluated) $\geq 4/6$, 6/12, 9/18, 11/24, and 13/30. The operating characteristics of this rule is found in table below.

Table 5. Operating Characteristics of Stopping Rules for Toxicity

True toxicity	P(stop)	p10	p25	p50	p75	p90	Avg # subjects	Avg # toxicities
0.10	0.002	34	34	34	34	34	33.9	3.4
0.20	0.035	34	34	34	34	34	33.2	6.7
0.30	0.196	12	34	34	34	34	29.9	9.0

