0.40	0.549	6	12	30	34	34	23.2	9.2
0.50	0.877	6	6	12	24	34	15.5	7.8

The Investigator is responsible for completing toxicity/efficacy summary reports and submitting them to the IND office Medical Affairs and Safety Group for review. These should be submitted as follows:

Toxicity Assessment: After the first 6 evaluable patients per cohort, complete 4 weeks of study treatment, and every 6 evaluable patients thereafter.

Efficacy Assessment: After the first 9 evaluable patients per cohort, complete 8 weeks of study treatment, and every 5 evaluable patients thereafter, until enrollment is complete. On every report submission, the response information from previous reported patients will need to be updated.

A copy of the cohort summary should be placed in the Investigator's Regulatory Binder under "sponsor correspondence".

Version Number: 1.8 Date: July 26, 2019

Proprietary of MD Anderson Cancer Center

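### The DLT period opens at first durvalumab, so related Grade 3-5 events confined to the three-week MEDI0457 lead-in never enter the toxicity stopping count; the expected effect is small and the correction cheap

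*Combined protocol and SAP*

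**What the plan says.** Section 6.7.2 ties a DLT to the "DLT evaluation period (i.e., 4 weeks after the first dose of durvalumab is administered for the initial six patients". The lettered items follow as examples within that definition, so they share its window. They include reactions that only the vaccine can cause (item k: "Grade 3 or greater injection site reaction that is persistent beyond 5 days") as well as related anaphylaxis (item n) and possibly related death (item o).

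Section 4.4.1 places MEDI0457 on Day 1 and in Weeks 3, 7 and 12. The antibody follows later: "Durvalumab will be administered on Week 4, Week 8, Week 12 and then every 4 weeks".

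Section 8.1.3 states that "DLT will be monitored continuously in cohorts of 6 subjects for all 34 subjects". The instruction is to "halt the trial if (# of patients with DLT) / (# patients evaluated") reaches 4/6, 6/12, 9/18, 11/24 or 13/30. It gives no definition of a DLT of its own and does not say who counts as evaluated. The toxicity report is due "After the first 6 evaluable patients per cohort, complete 4 weeks of study treatment, and every 6 evaluable patients thereafter".

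Section 1.6 lists possible responses when the first boundary is crossed. One is to "decrease the number of doses of vaccine given from a total of 3 to either 1 or 2 during the first 7 weeks".

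**The concern.** Section 8.1.3 is the plan's only quantitative stopping rule for toxicity. Two of the three vaccine doses in the first seven weeks fall before the DLT period opens. A related severe event that begins and ends in those three weeks is missing from the count, even though the response in Section 1.6 is partly aimed at those doses.

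The denominator is also open. Appendix E permanently stops both drugs for a Grade 4 site reaction, or for a Grade 3 reaction unchanged within 5 days. A patient stopped that way before Week 4 never enters the 6.7.2 period, and no text says whether he or she is evaluable for toxicity.

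Finally, the report in 8.1.3 is timed by weeks of study treatment, while the DLT period is timed from durvalumab. If the former is counted from Day 1, patients would be reported with most of their DLT period still unobserved.

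**Working it through.** **1. Clocks.** Week 4 Day 1 is Day 22, so the vaccine-only lead-in is Days 1-21 (18 to 24 days, given the ±3-day durvalumab window in Table 3). The 6.7.2 period is 28 days from Day 22, that is Days 22-49. Four weeks of study treatment counted from Day 1 end at Day 28. The overlap is Days 22-28, or 7 days, and the report would fall due 49 − 28 = 21 days before the period closes. The Week 7 vaccine dose (about Day 43) lies inside the period. A Week 3 reaction that persists past first durvalumab can arguably still count.

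**2. The plan's own figures.** The boundary at n patients is the smallest r with Pr(Beta(0.6 + r, 1.4 + n − r) > 0.30) > 0.90. This returns 4, 6, 9, 11 and 13 at n = 6, 12, 18, 24 and 30, as stated (posterior 0.945, 0.905, 0.951, 0.938 and 0.929; all below 0.90 with one event fewer). An exact binomial recursion over the five looks gives stopping probabilities of 0.0017, 0.0329, 0.1959, 0.5546 and 0.8751 at true rates of 0.10 to 0.50. Table 5 has 0.002, 0.035, 0.196, 0.549 and 0.877. The rule is computed correctly; the question is which events feed it.

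**3. Effect of counting lead-in events.** Let w be the rate in the 6.7.2 period and l the rate of qualifying lead-in events, taken as independent. The rate with both counted is 1 − (1 − w)(1 − l); for example, w = 0.30 and l = 0.05 give 1 − 0.70 × 0.95 = 0.335. The documents do not give l, so 1%, 2% and 5% are assumptions.

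| w | Lead-in not counted | l = 1% | l = 2% | l = 5% |
|---|---|---|---|---|
| 10% | 0.0017 | 0.0024 | 0.0033 | 0.0081 |
| 20% | 0.033 | 0.039 | 0.046 | 0.074 |
| 30% | 0.196 | 0.216 | 0.236 | 0.305 |

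If the reference to the initial six patients is taken literally and only the 4/6 look operates, the w = 30% row becomes 0.070, then 0.076, 0.082 and 0.102.

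**4. How plausible the assumed rates are.** Section 1.2.1 reports 20 patients given four doses each at this dose, with no related Grade 3 event and no event of Grade 4 or higher. Treating the 80 doses as independent, the one-sided 95% upper bound for two doses is 1 − 0.05^(2/80) = 7.2%. Treating the 20 patients as the units, the bound over four doses is 1 − 0.05^(1/20) = 13.9%. The assumed rates lie below both, but these bounds are only loose support.

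**5. A single-look illustration.** Four of six patients with qualifying events give a posterior of 0.945, which stops the cohort. If two of the four had lead-in events only, the count is 2/6, the posterior is 0.523, and the cohort continues.

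**The case against.** The strongest defence is that the window is deliberate. The combination is new (Section 1.3.1), and Section 1.4 names additive or synergistic toxicity as a risk. Combined exposure begins at first durvalumab. The vaccine alone already had reassuring experience: besides the 20 patients above, 551 VGX-3100 doses produced very few related Grade 3 events and no related Grade 4 events or SAEs. Because the Week 7 dose falls inside the window, item k and the dose-reduction option retain a function. This is a possible rationale, but the protocol does not state it. It also does not explain leaving out a related lead-in death, or a patient taken off both drugs before Week 4.

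A reader might infer that lead-in toxicity goes unmonitored. The documents do not support that. AEs and SAEs are recorded throughout (Section 7.4.1). Unexpected related fatal or life-threatening events are reported within 24 hours (7.2), and severe site reactions within 72 hours (7.6.6). Appendix E governs discontinuation. Section 1.6 also stages the start: "Once all 3 of these patients have completed the first 6 weeks of treatment, enrollment will be opened to all included cancer histotypes". What stands is narrower: none of these feeds the 8.1.3 count.

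A reader might also infer a flat contradiction between 6.7.2 and the report timing in 8.1.3. That depends on counting study treatment from Day 1. The term is not defined there, the paragraph sets a reporting date and does not define a DLT, and monitoring is described as continuous. It is an ambiguity to settle.

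**Conclusion.** The point holds as an inexpensive safety improvement with a small expected effect. On the natural reading of 6.7.2, a related Grade 3-5 event confined to the lead-in cannot reach the stopping boundary. One could read the four weeks as the end of a period that opens on Day 1, but no such start is written.

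The size depends on the window rate. At 10% the change is negligible, and at 20% it is about 0.6 to 4 percentage points. At the 30% limit it is 2 to 11 points. For rough scale, related Grade 3 or higher events on durvalumab alone were 10.0% in Section 1.2.2, over whole treatment and on a different schedule. A single related death would not cross 4/6 by itself.

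A reader might infer that the rule is badly weakened. With a true Day 1-49 rate of 40%, the stopping probability would fall from 0.555 to 0.397 if 10% of patients with events had them only in the lead-in, and to 0.033 if 50% did. No document supports shares of that size, and the vaccine experience points the other way. The boundaries and Table 5 are not in question.

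**What to change.** For the 8.1.3 count, in all monitored patients and not only the initial six, run the period from first MEDI0457 dose through 4 weeks after first durvalumab. Count a patient as evaluable if he or she has a qualifying related toxicity (6.7.2 items and exclusions) at any time in that period, even if durvalumab was never given, or completes the period without one. Report patients who leave early without an event separately, with a sensitivity count that includes them as non-events. Time the toxicity report to completion of the same period. Leave the boundaries, and the individual discontinuation rules in 3.4 and Appendix E, unchanged.

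This takes short edits to 6.7.2, to 8.1.3 and to its toxicity-report paragraph. No visits are added, because Table 3 already assesses adverse events at Weeks 1, 3, 4, 7 and 8.

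The costs are:

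- a slightly higher chance of stopping;
- a 30% limit applied to about 7 weeks instead of 4, without recalibration;
- a monitoring definition that differs from the DLT trigger in 3.4;
- a report about 3 weeks later than a Day 1 reading would give;
- a slight upward push on the observed rate if event-free early leavers are excluded, which the sensitivity count makes visible.
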